## SUBJECT PROCEDURES AND GUIDELINES

Please See Schedule of Events on Page 4 of this protocol.

### DATA COLLECTION

As mentioned above, we will collect clinical data from the chart, as well as data from the device per patients. Data could be, for example, what type of use did the patient practice with the device (call for help? communicate? listen to music or e-books?), for how long was the device worn, wakefulness timing and CAM-ICU results.

We will also collect the long-term results from the phone-based questioners.

Clinical data, as well as device-originating data, will be coded to allow de-identification during analysis, and stored in a HIPPA-compliant database (e.g., RedCAP).

### SUBJECT HOSPITAL DATA

- a) Consent material (study files)
- b) EyeControl measurement session data
- c) Demographic information: age, weight, height, gender, ethnicity
- d) Clinical status on admission (main diagnosis, procedures, or operations done)
- e) CAM-ICU
- f) Lab results, imaging, vitals, and charting during the ICU stay
- g) List of current medications, dose, and route of administration
- h) Medical history
- i) Previous and current head and brain imaging
- j) Previous and current EEG, if available
- k) Outcome measures: modified Rankin scale on discharge, discharge disposition, modified Rankin scale on follow-up clinic visits
- l) Responses of the patient and family members to a structured questionnaire regarding communication and use of the device
- m) Device training success and frequency for proficient utilization
- n) Eye photographs/video to explore possible relation to clinical events

Every study file will contain a fully signed consent form. The study files will be stored in a locked cabinet in a locked office.

### LONG-TERM OUTCOMES (LTO) BATTERY

Evaluations will be done using a specially-designed battery of tests that evaluates key aspects of functioning and behavior. This battery, which takes ~40 minutes to complete, will assess cognition, mental health (depression and PTSD), quality of life, and employment - all of which have been shown to be adversely affected in between 1/3 and 2/3rds of survivors of sepsis. The questioners will be executed by the Critical care, Brain Dysfunction and Survivorship (CIBS Center from Vanderbilt University). This battery has been successfully used by researchers in multiple studies at Vanderbilt Medical Center and elsewhere - it is well tolerated by patients, easy to administer and

to understand, and is very sensitive to the detection of even minor difficulties. Tests comprising the battery (by domain and name) are as follows: Cognition -Attention (Digit Span), Delirium (Telephone Confusion Assessment Method), Executive Functioning (Hayling Test), Language (Controlled Oral Word Association Test or COWA), Memory (Paragraph Recall from the Wechsler Memory Scale IV), Orientation (Telephone Interview for Cognitive Status), Reasoning (WAIS-IV Similarities); Functioning – Activities of Daily Living (Katz ADL), Employment (Employment Questionnaire), Instrumental Activities of Daily Living (Functional Activities Questionnaire); Mental Health - Depression (Beck Depression Inventory-II), PTSD (Post Traumatic Stress Disorder Checklist for the DSM V); Quality of Life – EQ5D.

## ELECTRONIC AND PAPER DATA COLLECTION SYSTEMS

REDCap is a secure online database for building and managing research data supported by Emory. All data collection will be input into the electronic data capture system. When subjects are enrolled, they will be sequentially assigned a unique subject code. This unique code will be used in the REDCap database. A centralized subject key that links subject identification with the unique subject code will be maintained in a secured and password protected electronic format.

**Data Handling** – For the duration of the study, the Investigator will maintain complete and accurate documentation including but not limited to medical records, study progress records, laboratory reports, case report forms, signed informed consent forms, correspondence with the IRB and adverse event reports, and information regarding subject discontinuation or completion of the study.

**Source Documentation** – Source documents are defined as original documents, data and records. Investigator will maintain source documents in the subject's medical records and/or subject binders, which confirm the data entered on the electronic case report forms.

**CRF Completion** – Data collection based on source-documented hospital and/or chart reviews will be performed accurately on the eCRFs by research personnel.

**Retention of Study Records** – Study records will be retained at all sites for a minimum of 3 years following the end of subject recruitment and follow-up activities.

**Data Quality** – Routine regulatory monitoring of regulatory compliance will be conducted by the Departmental Clinical Trials Regulatory Specialist.

## STATISTICAL ANALYSIS PLAN

**Step 1:** Step 1 of the present trial focuses on describing device usage and acceptability. Continuous data will be described using medians and interquartile ranges. Categorical variables will be described using frequencies, percentages, and 95% confidence intervals. No statistical hypothesis testing will be conducted.

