Outcome Measures	
For the burn-in phase, the primary outcome will be time to successful operation of the device (see below for definition), and secondary outcomes include length, type and intensity of use (e.g. use for communication, entertainment, call for help etc), safety, and proof of concept of non-communication features of the device such as wakefulness time monitoring and CAM-ICU capturing.
 
The primary end point of the second step will be number of alive and delirium days while in the ICU and on the ventilator up to 14 days from randomization, or to extubation or ICU discharge, the earliest. Secondary endpoints will include: proportion of patients who were able to operate and use EyeControl, the specific parameters of successful patients compared to those who were unable to operate it; the length and intensity of use; the correlation between the monitoring data and clinical data; and the cognitive and functional long term outcomes as assessed by telephone by the Critical care, Brain Dysfunction and Survivorship (CIBS Center from Vanderbilt University).

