### STEP 1:

**Primary Goal:** Assess the safety, tolerability, and ease of use of the EyeControl device. The outcome measure for this goal will be the time of training required for a patients to successfully execute two tasks using the device: call for help and choose a predefined sentence for the device to say three times straight.

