#### Secondary Goals:

1. Assess the proportion of mechanically ventilated, critically ill patients, with or without primary neurological injury, who could benefit and operate an eye-movement-tracking device as a means of communication.
2. Assess the type and length of the use done by the patient. For example, we will monitor how long a patient wears the device, uses it, and for what purpose (communication, call for help or entertainment).
3. Assess the EyeControl device as a diagnostic/monitoring tool for delirium in comparison to the bedside nurse assessment. Specifically, the device will record times of wakefulness for each 24h period of time, and will test for delirium using CAM-ICU. The later will be correlated with a live, verbal assessment done by a study team member.
4. Assess patient proficiency in device operation through daily orientation questionnaire.
5. Assess the change in level of frustration and discomfort patients and families feel in relation to communication with and without the device. These will be assessed by a questionnaire given to patients and families near their discharge.
6. Explore possible correlation between eye movements and clinical events by evaluating photographs of the eyes at the times of these events.

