#### STEP 1: ASSESS THE SAFETY, TOLERABILITY, AND EASE OF USE OF THE EYECONTROL DEVICE

On a daily basis all patients admitted to any of the ICUs at EUH will be screened for participating in the trial. Since during admission the patient could be first excluded and later meet inclusion criteria, the screening will continue for all patients on a daily basis (for inclusion/exclusion criteria, see below).

During screening, the patients' EMR will be accessed and/or their clinical status will be discussed with the treating team (RN, APP, MD) by a member of the study team in order to identify whether they meet inclusion/exclusion criteria. For example, the study-team personnel will identify if the patient is ventilated, for how long, and what is the patient's wakefulness and cooperation by nursing charting (e.g., RASS scale, nursing neurological and clinical assessment).

Of note, due to the different nature of neurologically injured patients in these settings (primary organ effected is the brain), we will enroll about 33-50% of the patients in this step from the neuroscience ICU. This approach will allow us to consider re-defining our parameters in the second step of the trial and design a pre-defined subgroup analysis.

Upon meeting inclusion criteria, patients and/or their LARs will be approached for consent (see below for consent process details). Consented patients will be instructed how to use and operate the EyeControl device. The primary outcome of this part of the study will be time to operate the device. Successful operation will be defined as the ability to use the device to call for help, and produce one predefined sentence out of several options, three different times.

Once the patient is able to operate the device, it will stay on the patient for as long as she or he would like it on, or until the patient is successfully extubated or discharged from the ICU, whichever is earliest. During the time the patient is wearing the device, apart from its original intention to serve as a communication device, the following features will be activated and tested:

- a. Emergency call—if the patient is in distress, she or he could call for help by simply blinking three times. This will initiate a call for help from the device. We will monitor the use of this emergency call, its frequency, and causes for calling.

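### The Step 1 plan does not say how patients who never operate the device enter the primary time outcome; by default its median describes successes only and is biased towards faster learning.

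*Combined protocol and SAP*

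**What the plan says.** Three places define the Step 1 primary outcome as a time that ends in success:

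- Synopsis, Outcome Measures: "the primary outcome will be time to successful operation of the device".
- Study Purpose, Step 1: "The outcome measure for this goal will be the time of training required for a patients to successfully execute two tasks using the device".
- Study Design and Methods, Step 1: "The primary outcome of this part of the study will be time to operate the device".

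The Statistical Analysis Plan for Step 1 does not mention this outcome. It has one rule for continuous data, "Continuous data will be described using medians and interquartile ranges", and one for categorical data, "Categorical variables will be described using frequencies, percentages, and 95% confidence intervals". It adds: "No statistical hypothesis testing will be conducted".

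No section assigns a value to a patient who never succeeds. None says how extubation, ICU discharge, death, re-sedation or stopping training before success is handled. The multiple-imputation rule is written under Step 2.

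The plan does foresee failures. The first Step 1 secondary goal is to "Assess the proportion of mechanically ventilated, critically ill patients, with or without primary neurological injury, who could benefit and operate an eye-movement-tracking device". Among the Step 2 secondary endpoints, the Synopsis lists "the specific parameters of successful patients compared to those who were unable to operate it".

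**The concern.** Time to success exists only for patients who succeed. A median and IQR of the recorded times therefore leaves out everyone who did not learn to use the device, and those are the patients for whom it was hardest. The main Step 1 figure for ease of use would then describe a group selected on the outcome itself.

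Failures are plausible in this population. The Sample Size section wants at least a third of Step 1 to come from the neuroscience ICU, specifically patients with acute brain injury. The Step 2 design text accepts that patients may need moderate to deep sedation after enrolment. A reader who sees only a median time to operate the device could take it as the typical experience of an enrolled patient.

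**Working it through.** **No stated figure to reproduce.** Step 1 is descriptive, with no power calculation and no expected success rate for this trial. The only success figure in the documents is the manufacturer's report of nearly 100% at another centre (Eye-Control Device section). The check therefore concerns the direction and possible size of the bias.

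**Inputs**
- Step 1 sample size: up to 60 (Sample Size section).
- Failure share f: not given; assumed from 2% to 50%.
- Distribution of times among successes: not given; assumed log-normal with log-SD σ between 0.5 and 1.2.

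**Direction.** Rank each non-succeeder as slower than every success. The all-patient median is then the 0.5/(1−f) quantile of the success times, and the all-patient upper quartile is the 0.75/(1−f) quantile. Whenever f > 0 both lie above the corresponding successes-only quantiles. The median does not exist once 0.5/(1−f) reaches 1, at f = 50%. The upper quartile does not exist from f = 25%.

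By counting, with 60 patients and 12 failures (f = 20%), the successes-only median lies at the 24th–25th of 48 recorded times. The all-patient median lies at the 30th–31st, and 30/48 = 0.625 = 0.5/0.8.

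**Size.** Under the log-normal assumption the ratio of all-patient to successes-only value is

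- median: exp(σ × z(0.5/(1−f)))
- upper quartile: exp(σ × [z(0.75/(1−f)) − z(0.75)])

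For example, at f = 10%, 0.5/0.9 = 0.556 and z = 0.140. The median ratio is exp(0.5 × 0.140) = 1.07 at σ = 0.5 and exp(1.2 × 0.140) = 1.18 at σ = 1.2.

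| Failure share f | Success quantile that is the all-patient median | Median ratio, σ 0.5 to 1.2 | Upper-quartile ratio, σ 0.5 to 1.2 |
|---|---|---|---|
| 2% | 0.510 | 1.01–1.03 | 1.02–1.06 |
| 5% | 0.526 | 1.03–1.08 | 1.07–1.17 |
| 10% | 0.556 | 1.07–1.18 | 1.16–1.42 |
| 20% | 0.625 | 1.17–1.47 | 1.54–2.81 |
| 30% | 0.714 | 1.33–1.97 | not reached |
| 40% | 0.833 | 1.62–3.19 | not reached |
| 50% | 1.000 | not reached | not reached |

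**Simulation check.** With n = 60, σ = 0.8 and a success median of 10 units, the successes-only median stayed near 10.1 at 10%, 20% and 30% failure. The all-patient median was 11.2, 12.9 and 15.7, matching the formula (10 × 1.12, 1.29 and 1.57).

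**Precision of the success proportion.** With 60 patients, 54 successes give a Wilson 95% CI of 80–95%, and 48 give 68–88%.

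**The case against.** The plan is silent; it does not say that failures are excluded. A reader might infer an exclusion rule from the median-and-IQR sentence, but that sentence is generic, and a median can include failures if they are ranked last. This stands: exclusion is the default outcome of the wording, not a stated choice. Even on the charitable reading the plan is incomplete, because it does not say what is reported when the upper quartile or median is not reached.

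The success proportion is already a secondary goal and would be shown with a 95% CI. A success proportion together with learning time among successes is a legitimate two-part description. This stands in part. The proportion makes failures visible, but the plan neither labels the time outcome as conditional on success nor ties the two together. The Subject Withdrawal section also removes some early withdrawals from cohort totals, so the proportion may not count everyone either.

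The effect may be negligible. The exclusion criteria remove patients who cannot follow simple eye commands, blink or move their eyes, and the manufacturer reports near-complete success. At 2% failure the median moves by only 1–3%. This stands as a limit on size, although a company report from general ICU settings elsewhere is weak support for a sample with many brain-injured patients.

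Patients extubated before success may be recovering well and are not necessarily poor learners. This is fair. The all-patient measure describes how soon patients come to operate the device while they are still ventilated in the ICU. It does not measure learning ability alone.

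**Conclusion.** The point holds as a gap with a predictable direction. The primary time outcome has no rule for patients without a success time, and the default analysis can only understate the all-patient learning time. The size cannot be fixed from the documents, because the failure rates and the log-normal spread used here are assumptions. The effect is trivial if nearly all patients succeed, material at about 20% failure (median 17–47% higher), and large enough to make the upper quartile unattainable from 25%.

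A reader might go further and infer that this median feeds the design of Step 2. The documents do not support that. Step 1 as a whole is meant to give experience before Step 2, but no Step 2 parameter or go/no-go rule uses this number, and the Step 2 sample size comes from a published observational study. What is at stake is how Step 1 itself is reported.

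**What to change.** Add to the Step 1 part of the Statistical Analysis Plan, in substance:

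> Time to successful operation is analysed in all patients who start training. The clock is [training minutes / elapsed time from start of training; state one]. Results are shown as a cumulative incidence curve of success, with extubation, ICU discharge, death, or stopping training for any reason (including re-sedation or withdrawal) before success as competing events. The median and quartiles are reported, or given as not reached, together with the proportion successful and its 95% CI.

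With every patient followed to success or a competing event, ranking non-succeeders as longer than any success gives the same median and quartiles, and may be simpler for up to 60 patients. A successes-only median can still be shown if labelled as such.

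The definition of success also needs reconciling. Study Purpose, Step 1 asks for the sentence task three times in a row, whereas Study Design and Methods, Step 1 asks for it on three separate occasions. The choice determines when the clock stops and who counts as unsuccessful.

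The cost is a short paragraph and slightly more analysis, with no extra patients or visits. The start of training and the time and reason for stopping must be recorded for every patient. The reported time may look less favourable.

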### Step 2:

Primary Outcome: The time spent alive and non-delirious in the ICU

Covariates/Confounders: age, gender, race, baseline education level, unit to which the patient was admitted to, need for tracheostomy, severity of illness by SOFA or APACHE score on admission and randomization day, categorical reason for admission (e.g. sepsis, ARDS, elective surgery, stroke etc), diagnosis of delirium prior to randomization and the presence of an acute central neurological injury.

Unadjusted Analyses: The time spent alive and non-delirious in the ICU will be evaluated using the stratified variant of the Mann-Whitney U test. In this analysis, patients will be stratified by ICU setting. For other variables, the unadjusted comparison will depend on the type of variable. In general, continuous variables will be compared using a Mann-Whitney U test and categorical variables will be compared using the  $\chi^2$  test.

Adjusted Analyses: The time spent alive and non-delirious in the ICU will be evaluated using a multi-level/mixed-effects quantile regression (median/50th percentile) while controlling for the previously listed covariates. The multi-level/mixed-effects model will be used to account for clustering within ICU setting. In the event that the regression fails to estimate properly, the covariates will be used to generate propensity scores and patients will be stratified into  $\geq 5$  propensity score strata. The time spent alive and non-delirious in the ICU will then be analyzed using the stratified variant of the Mann-Whitney U test. Analyses of the secondary outcomes will depend on the type of variable. Continuous variables will be analyzed using multi-level/mixed-effects quantile regressions (median/50th percentile), binary variable will be analyzed using multi-level/mixed-effects binary logistic regressions, ordinal scales will be analyzed using multi-level/mixed-effects ordinal (cumulative logit) logistic regressions.

Missing Data: In the event of substantial missing data, data will be imputed using a multiple imputation procedure. The type of procedure (e.g. fully conditional specification, hot decks etc.) and the number of imputed data sets will be determined by the amount of missing data and the pattern of missingness.

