### DELIRIUM IN THE ICU

One of the dreaded complications in critically ill patients is delirium. Delirium is an acute form of encephalopathy, or brain dysfunction, that is manifested by waxing and waning changes in cognitive abilities during acute illness. Delirium is diagnosed in 48-83% of critically ill patients (Girard et al., 2018, Ely et al. 2001), and is linked to increased mortality (Ely et al., 2004). Several risk factors associated with delirium include older age, prior neurological injuries or neurodegenerative disorders, as well as the acuity of illness and admission in the ICU (Ely et al., 2001; Oldham et al., 2018). Disorganized sleep is also linked to higher risk of delirium (Dres et al., 2019; Marra et al., 2019a). Delirium is strongly correlated with worse outcomes, including longer length of stay in the ICU and the hospital, and increased mortality (Marra et al., 2019b). Treatment for delirium includes pharmacological (mostly anti-psychotic medications) and non-pharmacological interventions (Marra et al., 2019). Non-pharmacological interventions to prevent and treat delirium include early mobilization, frequent reorientation, etc. (Martínez et al., 2017). Recently, a large randomized controlled trial failed to show benefit for pharmacological interventions to treat and prevent delirium, leaving non-pharmacological interventions as the main treatment option for now (Girard et al., 2018). Lack of effective communication not only could impair such non-pharmacological interventions but limit the diagnosis of delirium in the first place (Rowley-Conwy, 2018). However, from a diagnostic stand point, others have shown a valid method to diagnose delirium even in mechanically ventilated patients (Ely et al., 2001).

[figure not shown]

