### STEP 2:

**Primary goal:** Measure the time spent alive and non-delirious in the ICU up to 14 days from randomization with EyeControl-based communication compared with the standard of care, in a randomized-controlled fashion.

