As part of its operation, the device captures photographs and video of the patient's eyes (figure 3). In addressing the secondary goal of potential correlation between eye behavior and clinical events, we will explore this possibility by evaluating photographs of the eyes at the times of clinical events (i.e. hypoxia, new onset shock, or new onset sepsis). The device will activate the image data collection only after 50 consecutive frames of eye-in-the-image. This should be a safety index to verify that the device is only recording the eye. It will stop recording immediately when non-eye-in-the-image occurs. Data processing to decide if an eye is in the image is done locally on the device, so eventually only images of eyes should be collected. All external image data processing will be done following deidentification of the data, using the patient code only as an identifier.

Figure 3. Example photographs captured by the EyeControl device.

No randomization or blinding is planned for this step of the study, and no samples are planned to be collected.

---

**STEP 2: MEASURE REDUCTION IN DELIRIUM-FREE AND ALIVE DAYS IN THE ICU WITH EYECONTROL-BASED COMMUNICATION COMPARED WITH THE STANDARD OF CARE.**

The second step will be similar to the operation of the first one, in terms of patient screening and enrolling. The main difference will be the randomization process. Patients will be randomized to use EyeControl for as much as they wish, versus the standard of care. Randomization will be done centrally, and will be stratified to the specific unit, gender and age, race and ethnicity.

The primary goal of the second step will be to measure the time spent alive and non-delirious in the ICU with EyeControl-based communication compared with the standard of care. Delirium will be defined as CAM-ICU positive, starting at day 1 of use (following the day of training), up to 14 days from randomization or ICU discharge, the earliest. However, patients could require moderate to deep sedation following randomization, for example due to new or evolving medical complication. Whenever the RASS is below (-1), CAM-ICU will not be measured, and will be charted as undetermined. Therefore, only days in which the patient will be CAM-ICU positive, will be counted towards the primary outcome. CAM-ICU positive days prior to randomization will not be counted towards the primary outcome.

[figure not shown]
The secondary outcomes will include the following:

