## SAMPLE SIZE

From our retrospective analysis (described in the introduction), we expect about 130 patients per month for the initial screening (ventilated for at least two days). The same patient could be ineligible on a certain day, but become eligible later in the admission (e.g., due to the severity of the illness, the patient is deeply sedated for the first few days, and later sedation is weaned). This will allow us to recruit more patients, at different time points of their admission. Even with this in mind, it would be reasonable to assume that about half of these initially screened patients will not be eligible at any point of their admission due to any one of the exclusion criteria. Of those who will be eligible, we expect a high rate of consent, due to the low risk and the potential benefit of using the device while in the ICU. We therefore expect a rate of about 30 patients a month to be enrolled.

For the first step, we will plan to enroll up to 60 patients, and at least a third of the sample will be from the neuroscience ICU, and specifically patients with an acute brain injury

Given that there are no prior data, there is no clear criteria that would justify a specific number. We believe that having 40 to 60 patients work with this new device would be sufficient to draw initial conclusions about its use and specific indications according to the study aims as stated above.

For the second part of the trial, power calculations are based on previously published BRAIN-ICU trial. In that observational trial patients had  $6.8 \pm 5.2$  delirium/coma-free days within the first 14 days of admission, with an overall rate of about 50% rate of delirium. For the present trial, we considered a 2 day reduction in the time spent delirious as clinically significant. Given these parameters, the present trial will require 248 patients ( $N = 124$  per arm) to achieve sufficient power (80%,  $\alpha = .05$ ) to detect a 2 day difference. In general, a sample size of 248 will provide sufficient power to detect a standardized mean difference of 0.38 (assuming minimal asymptotic relative efficiency of Mann-Whitney U test), an odds ratio of 2.14 for binary variables (assuming maximal variance for a binomial distribution), and a Cohen's  $f$  of 0.18.

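### The Step 2 primary outcome credits non-delirious days only up to ICU exit, so early recovery scores low and ties with early death, and a delirium benefit is diluted if the device also shortens the stay

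*Combined protocol and SAP*

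**What the plan says.** The SAP, Step 2, names the endpoint: "Primary Outcome: The time spent alive and non-delirious in the ICU". The Step 2 primary goal under Study Purpose agrees and adds the cap: "Measure the time spent alive and non-delirious in the ICU up to 14 days from randomization".

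Two stopping rules are given. Study Design and Methods, Step 2, counts "up to 14 days from randomization or ICU discharge, the earliest". The synopsis (Outcome Measures) counts "while in the ICU and on the ventilator up to 14 days from randomization, or to extubation or ICU discharge, the earliest".

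The same Step 2 design section also holds a different counting rule: "only days in which the patient will be CAM-ICU positive, will be counted towards the primary outcome". The synopsis likewise speaks of delirium days rather than delirium-free days. Days with RASS below -1 are charted as undetermined.

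No section credits a day after ICU discharge or extubation, gives death a worst score, or treats death and discharge as competing events. The SAP ranks patients on the count with a Mann-Whitney test stratified by ICU, and models its median in the adjusted analysis.

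The Sample Size section plans on 6.8 ± 5.2 "delirium/coma-free days within the first 14 days of admission" and a 2-day difference.

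**The concern.** On an outcome analysed by ranks, a higher value has to mean a better course. Here the count is bounded by how long the patient stays under observation, and that length is itself an outcome. Leaving the ICU well and dying early both end the count, and the plan does not tell them apart, although being alive is part of the endpoint's name.

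The background section gives a reason to expect the two components to move together: "Delirium is strongly correlated with worse outcomes, including longer length of stay in the ICU". If the device reduces delirium and some patients leave sooner as a result, part of the gain is taken back by the shorter counting window. Conversely, an intervention that only prolonged the stay of non-delirious patients would look beneficial. A null, positive or negative primary result would then be hard to interpret.

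**Working it through.** **The plan's own figure.** Inputs from Sample Size: difference 2 days, SD 5.2, power 80%, alpha .05 (taken as two-sided), minimal Mann-Whitney efficiency (0.864). Normal approximation: 2 × (5.2 × (1.960 + 0.842) / 2)² = 106.1, so 107 per arm. Then 107 / 0.864 = 123.8, so 124 per arm and 248 in total. The stated N reproduces. Its inputs are stated as a count over 14 days, not a count that stops at ICU exit.

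**Ranking of single patients.** ICU-only score = counted ICU days − delirious days. Fixed-window score = days alive within 14 − delirious days. The exit day is counted, and no day is undetermined.

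| Patient | ICU-only | CAM-ICU positive days | Fixed 14 days |
|---|---|---|---|
| Never delirious, discharged alive day 4 | 4 − 0 = 4 | 0 | 14 − 0 = 14 |
| Never delirious, dies day 4 | 4 − 0 = 4 | 0 | 4 − 0 = 4 |
| 14 ICU days, 8 delirious | 14 − 8 = 6 | 8 | 14 − 8 = 6 |

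The ICU-only count puts the third patient first and ties the first two. Counting positive days instead, where fewer is better, gives the early death 0, the best possible value.

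**Effect on an arm difference.** Gain in ICU-only score = delirious days prevented − counted days lost. Take the 2-day target with a stay 2 days shorter:
- Control: 8 ICU days, 4 delirious. ICU-only 8 − 4 = 4; fixed window 14 − 4 = 10.
- Device: 6 ICU days, 2 delirious. ICU-only 6 − 2 = 4; fixed window 14 − 2 = 12.
- Difference: 0 on the ICU-only count, 2 on the fixed window.

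Counting positive days gives 4 against 2, so nothing cancels under that rule.

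**How far it depends on the stay.** The documents give no figure for how much the stay shortens, so this is illustrative. Assumptions: 124 per arm, gamma-distributed stay with mean 9 days, half ever delirious, up to 4 delirious days removed, no deaths, 600 runs. Rejection rate for the ICU-only count, by days of stay lost per delirious day prevented:

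| 0 | 0.25 | 0.5 | 0.75 | 1.0 |
|---|---|---|---|---|
| 95% | 84% | 56% | 23% | 7% |

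A second no-death run gave 98%, 56% and 5% at 0, 0.5 and 1.0.

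**With deaths.** Assumptions: 20% deaths, delirium in 50%, mean 8 delirious days cut to 4 in those affected, mean 5 clear ICU days in control, unstratified Mann-Whitney test, 1,000 runs.
- Stay shortened only by the delirious days prevented: ICU-only 3.75 vs 4.26 (gain 0.51), benefit in 30% of runs; fixed window 8.65 vs 10.08 (gain 1.43), 37%. This is dilution rather than cancellation, because for stays cut off at day 14 or by death, fewer delirious days leave room for clear ones.
- Clear stay also 1 day shorter: ICU-only 3.78 vs 3.49, benefit in 0.7% and significant harm in 5.4%; fixed window benefit in 32%.
- Clear stay 2 days shorter: ICU-only 3.78 vs 2.66, significant harm in 72%; fixed window benefit in 28%.
- No delirium effect, discharge 2 days faster: ICU-only shows significant harm in 93%.

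**The case against.** **The counting rule is not settled.** If the rule in the Step 2 design section governs and only CAM-ICU positive days count, early recovery is not penalised and nothing cancels. This stands. It limits the point to the definition in the SAP and the Step 2 primary goal. The death problem remains under either rule, and the conflict itself needs resolving.

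**Cancellation is conditional.** A reader might infer that the endpoint will hide a real benefit. The documents do not support that. They report a correlation between delirium and length of stay, not a causal day-for-day effect. With stay unchanged, the ICU-only count detects the benefit (95% in the no-death model).

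**The fixed window is not a guarantee of power.** A no-death, one-for-one illustration gives 9% rejection for the ICU-only count and 99% for the fixed window. It is tempting to read these as the power of the two endpoints, but they are an extreme case. With the plan's SD of 5.2 and a 1.6-day difference, normal-approximation power at 124 per arm is about 68% before the Mann-Whitney penalty. The model with 20% deaths gave 28% to 37% in the scenarios above where delirium fell.

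**An on-treatment window is a recognisable choice.** In Step 1 the device stays on at most until extubation or ICU discharge, and Step 2 is said to operate similarly. That could explain the stop, but the plan does not argue it, and it does not repair the ranking or the tie with death.

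**A fixed window has its own weakness.** CAM-ICU is scheduled only at screening and during the ICU admission. Crediting unassessed later days could favour the arm discharged earlier, in an open-label trial. This stands and has to be handled in the fix.

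**Conclusion.** The point holds in conditional form. Under the definition in the SAP and the Step 2 primary goal, a higher score does not reliably mean a better outcome. An early live discharge can rank below a long, partly delirious stay and ties with an early death that has the same number of delirious days. Those two results follow from the definition alone, without simulation.

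The loss of a treatment effect depends on how far the device shortens counted time: none if stay is unchanged, complete at one counted day per delirious day prevented, and a reversal beyond that. The documents do not say where in that range the trial will fall, and all simulated percentages rest on assumed inputs.

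The alternative rule in the protocol exchanges one fault for another, since early death then scores best. The sample size is arithmetically sound, but it is planned on a count stated over 14 days, which is not the endpoint the SAP defines.

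**What to change.** Reconcile the synopsis, the Step 2 primary goal, the Step 2 design section and the SAP to one primary outcome: days alive and free of delirium over the same 14 days from randomization for every patient, with these scoring rules.
- Days after death score 0.
- Days alive after ICU discharge or extubation count as delirium-free unless a charted CAM-ICU is positive.
- Undetermined days (RASS below -1) do not count as free, in line with the delirium/coma-free planning figure.

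Report the ICU-only count as secondary. Add a sensitivity analysis that carries the last CAM-ICU status forward for patients discharged from the ICU while delirious.

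The cost is wording in the protocol and SAP plus that one analysis. Discharge data and mortality are already collected. N stays at 248 if the 2-day difference and SD of 5.2 are kept. The match to the planning figure is closer but not exact, since that figure runs from admission rather than randomization. The remaining downside is that delirium after ICU discharge is not assessed on schedule; the sensitivity analysis shows how much this matters but does not remove it.
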